**5.5 Outcomes of Interest**

- Respiratory illness-associated hospitalizations with laboratory-confirmed influenza
  - Respiratory hospitalizations will be defined using ICD-9 and ICD-10 discharge diagnoses codes as listed in Appendix D.
  - Data on all respiratory hospitalizations will be collected for the entirety of the surveillance period (influenza season).
  - The respiratory hospitalizations will be linked with data on influenza testing to determine if the hospitalization was associated with laboratory-confirmed influenza.
    - Laboratory-confirmed influenza associated respiratory hospitalization will be defined by a positive influenza test within 14 days prior to hospitalization or no more than 3 days after hospital admission.

- Hospitalization will be defined as admission to an inpatient ward or an observation unit. Time spent only in the emergency department will not count as a hospitalization.
- Re-admissions that occur within 30 days of the index hospitalization will be counted as part of the index hospitalization. Readmissions that occur >30 days after the index hospitalization will be considered new hospitalization events.
- ICU admission among persons hospitalized with laboratory-confirmed influenza-associated respiratory hospitalization
- Invasive mechanical ventilation among persons hospitalized with laboratory-confirmed influenza-associated respiratory hospitalization
- In-hospital death among persons hospitalized with laboratory-confirmed influenza-associated respiratory hospitalization
- Acute respiratory illness-associated outpatient visits with laboratory-confirmed influenza
  - Acute respiratory illness-associated outpatient visit will be defined using the ICD-9 and ICD-10 discharge codes listed in Appendix D.
  - Data on all acute respiratory illness-associated outpatient visits will be collected for the entirety of the surveillance period (influenza season).
  - The acute respiratory illness outpatient visit will be linked with data on influenza testing to determine if the visit was associated with a positive influenza laboratory test.

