***Objective 5: Assessment of vaccine effectiveness***

- We will estimate the effect of influenza vaccination on risk of lab-confirmed influenza-associated respiratory hospitalization by age group, influenza type/subtype, and high-risk conditions
  - The risk of influenza-associated respiratory hospitalization among cohort members who were or were not vaccinated with the current season influenza will be compared using appropriate methods for longitudinal data with time varying exposure, including Poisson regression or proportional hazards modeling.
  - VE will be estimated as  $(1 - \text{adjusted relative risk}) \times 100$ .
  - We will assess and adjust for confounders as appropriate. These may include characteristics such as age, sex, site, race/ethnicity, high-risk health conditions, prior healthcare utilization, time of event during the influenza season, etc.
  - Data collected for this study are intended to be pooled across sites. VE will first be estimated for each site and heterogeneity in estimated VE across sites examined.
- We will estimate the effect of influenza vaccination on risk of lab-confirmed influenza-associated ARI outpatient visit among children (adults only if influenza testing allows for this) by age group, influenza type/subtype, and high-risk conditions
  - The risk of influenza-associated outpatient visits among cohort members who were or were not vaccinated with the current season influenza will be compared using appropriate methods for longitudinal data with time varying exposure, including Poisson regression or proportional hazards modeling.
  - VE will be estimated as  $(1 - \text{adjusted relative risk}) \times 100$ .

- We will assess and adjust for confounders as appropriate. This may include characteristics such as age group, sex, site, race/ethnicity, high-risk health conditions, prior healthcare utilization, time of event during the influenza season, etc.
- Data collected for this study are intended to be pooled across sites. VE will first be estimated for each site and heterogeneity in estimated VE across sites examined.
- VE analyses against influenza-associated respiratory hospitalizations will also be conducted using a test-negative case-control design
  - This analysis will be conducted among individuals who were hospitalized for acute respiratory illness during the influenza season and who were tested for influenza.
  - Cases will be defined as hospitalized individuals who tested positive for influenza.

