  - Controls will be defined as hospitalized individuals who tested negative for influenza.
  - Influenza vaccination status will be determined for all cases and controls and the odds of vaccination will be compared using logistic regression.
  - VE will be estimated as  $(1 - \text{adjusted odds ratio}) \times 100$ .
  - We will assess and adjust for confounders as appropriate. This may include characteristics such as age group, sex, site, race/ethnicity, high-risk health conditions, prior healthcare utilization, time of event during the influenza season, etc.
  - Data collected for this study are intended to be pooled across sites. VE will first be estimated for each site and heterogeneity in estimated VE across sites will be examined.

Beyond the primary objectives listed here, additional analyses may be pursued and will be considered by the joint steering committee.

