## Respiratory Outpatient Visits and Hospitalizations

Respiratory outpatient visits and hospitalizations will be defined using the following ICD-9 and ICD-10 diagnosis codes. Codes can be in any position. For hospitalizations, only discharge codes should be considered. Encounters occurring in the outpatient clinic, emergency department, urgent care, or via telehealth should additionally include encounters with codes related to signs/symptoms (at the bottom of the table).

| Description   | ICD-10*
code |
|--|-------------------------|
| Pulmonary anthrax  | A22.1*                  |
| Whooping cough   | A37*                    |
| Other specified sepsis   | A41.89                  |
| Legionnaire's Disease  | A48.1*                  |
| Cytomegaloviral pneumonitis  | B25.0*                  |
| Viral infection of unspecified site  | B34 *                   |
| Aspergillosis  | B44 *                   |
| Adenovirus   | B97.0*                  |
| Enterovirus  | B97.1*                  |
| Coronavirus  | B97.2*                  |
| Respiratory syncytial virus as the cause of diseases classified elsewhere                | B97.4*                  |
| Other viral agents as the cause of diseases classified elsewhere                         | B97.8*                  |
| Acute suppurative otitis media   | H66.0*                  |
| Suppurative otitis media, unspecified  | H66.4*                  |
| Otitis media, unspecified  | H66.9*                  |
| Otitis media in diseases classified elsewhere  | H67 *                   |
| Diseases of the respiratory system   | J00-J99 *               |
| Other viral diseases complicating pregnancy, childbirth and the puerperium               | O98.5*                  |
| Diseases of the respiratory system complicating pregnancy, childbirth and the puerperium | O99.5*                  |
| COVID-19   | U00                     |
| COVID-19   | U07.1                   |
| COVID-19   | U49                     |
| Encounter for observation for suspected exposure to biological agents ruled out          | Z03.81 *                |
| Encounter for observation for other suspected diseases and conditions ruled out          | Z03.89 *                |
| Encounter for screening for respiratory tuberculosis                                     | Z11.1 *                 |
| Encounter for screening for other bacterial diseases                                     | Z11.2 *                 |

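### Entry to the test-negative hospitalization analysis depends partly on the influenza result, because a case can qualify on an influenza discharge code alone

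*Protocol*

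**What the plan says.** Protocol section 6.1, Objective 5, sets the population of the test-negative analysis: "This analysis will be conducted among individuals who were hospitalized for acute respiratory illness during the influenza season and who were tested for influenza". The split is by result: "Cases will be defined as hospitalized individuals who tested positive for influenza" and "Controls will be defined as hospitalized individuals who tested negative for influenza".

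Section 5.5 says how a respiratory admission is recognised: "Respiratory hospitalizations will be defined using ICD-9 and ICD-10 discharge diagnoses codes as listed in Appendix D". The title of Appendix D says that it also serves to define ARI hospitalizations, so the same list governs entry here.

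Appendix D then fixes three things:

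- Position: "Codes can be in any position".
- Timing: "For hospitalizations, only discharge codes should be considered".
- Content: the table includes the row "Diseases of the respiratory system | J00-J99" with no exception for influenza. The rows for cough, fever, malaise and similar signs are added only for outpatient clinic, emergency department, urgent care and telehealth encounters.

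In section 5.5 a laboratory-confirmed influenza admission is "defined by a positive influenza test within 14 days prior to hospitalization or no more than 3 days after hospital admission".

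**The concern.** A test-negative comparison rests on choosing patients by a rule that does not look at the test result, so that cases and controls come from one pool of tested admissions. Under the window in section 5.5 the result will normally be known before discharge codes are assigned, and an influenza code is assigned because of a positive result. Counting that code as sufficient for entry lets the result open the door for cases. No corresponding door is open to a negative patient whose only other codes are fever or cough.

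At stake is one of the two stated analyses of VE against influenza-associated hospitalization under primary Objective 5. Restricting to tested patients does not help, because both patients were tested. Objective 3 examines who is tested among respiratory hospitalizations already selected by these codes, so that part of it would not see the negatives that the rule leaves out.

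**Working it through.** The protocol gives no figure for the test-negative analysis. Table 1 concerns person-years for VE against severe outcomes, so there is nothing to reproduce. The check has two parts.

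**1. Entry logic.** Four kinds of tested inpatient, traced through section 5.5, section 6.1 and Appendix D:

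| Other discharge codes | Positive, coded as influenza | Negative |
|---|---|---|
| Another J00-J99 code, e.g. asthma or COPD | enters as case | enters as control |
| A listed code outside J00-J99, e.g. B34, H66.0, Z03.89, Z11.x, Z20.x | enters as case | enters as control |
| Only sign or symptom codes, e.g. R50 or R04-R09 | enters as case | does not enter |
| No listed code at all | enters as case | does not enter |

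The first two rows are symmetric. The last two are not, and nothing printed in the protocol removes the difference.

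**2. Possible size.** Call admissions with another listed code R, and admissions with none N.

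Inputs:

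- p, coverage among R controls. Section 6.2 assumes 30%, 42% and 65% in three equal adult age groups, so p = (30 + 42 + 65)/3 = 45.7%. For children, (70 + 50)/2 = 60%.
- q, share of cases that enter only on an influenza code. Not given; assumed 5% to 30%.
- k, vaccination odds in N relative to R. Not given; assumed 0.5 to 2.
- True VE, taken as 40% or 20% and the same in R and N.

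Formulas:

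- Case odds of vaccination in R = (1 - VE) × p/(1 - p); in N, k times that.
- Vaccinated proportion of all cases = (1 - q) × proportion in R + q × proportion in N.
- Observed VE = 1 - (odds in all cases) / (p/(1 - p)).

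Worked line, adults, true VE 40%, q = 10%, k = 0.5:

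- Control odds 0.4567/0.5433 = 0.8405.
- R case odds 0.6 × 0.8405 = 0.5043, proportion 0.3352.
- N case odds 0.2521, proportion 0.2014.
- Mixed proportion 0.9 × 0.3352 + 0.1 × 0.2014 = 0.3218, odds 0.4746.
- Observed VE = 1 - 0.4746/0.8405 = 43.5%.

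Observed VE (%), adults, true VE 40%:

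| q | k = 0.5 | k = 0.67 | k = 1 | k = 1.5 | k = 2 |
|---|---|---|---|---|---|
| 5% | 41.8 | 41.1 | 40.0 | 38.7 | 37.7 |
| 10% | 43.5 | 42.2 | 40.0 | 37.4 | 35.4 |
| 20% | 46.9 | 44.3 | 40.0 | 34.7 | 30.5 |
| 30% | 50.2 | 46.4 | 40.0 | 31.9 | 25.4 |

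With a true VE of 20%, q = 10% gives 24.9% (k = 0.5) and 14.1% (k = 2). With paediatric coverage of 60% and a true VE of 40%, q = 10% gives 43.8% and 35.8%.

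All values are before covariate adjustment. The column k = 1 shows no bias at any share. If cases and controls are both limited to R, the formula returns the true VE. If both include N, it does so after stratifying on R and N.

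**The case against.** Several points on the other side are sound.

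- **The affected group may be small.** Codes count in any position across the whole respiratory chapter, so a febrile or cardiac admission with asthma, COPD or another respiratory code as a secondary diagnosis enters whatever its result. The upper shares in the table are assumptions and may be far too high.
- **Adjustment may absorb part of it.** Section 6.1 lists age group, high-risk conditions, prior utilization and timing as possible confounders, and these are likely correlates of any coverage difference. Entry route is not among them.
- **The list is not final.** Appendix D calls its codes examples that may be modified and refers to a codebook for the full list, which was not available. Only the protocol was at hand. The block J00-J99 is nevertheless printed as included.
- **Nothing is lost in the data.** Section 5.6 extracts diagnosis codes for all hospitalizations with respiratory virus testing, so other entry rules can be run later. This makes the remedy cheap; it does not make the printed rule symmetric.

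A reader might infer more than the document supports. That VE *is* biased does not follow, since the effect is zero when vaccination odds are equal across entry routes. That controls need a respiratory code is too narrow: viral, otitis, observation, screening and exposure codes are also listed, and some would suit a patient screened and found negative. That cases and controls come from different admissions is true only of cases with no other listed code.

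Nor does it follow that influenza codes should simply be struck from the primary rule. A coder may record a respiratory presentation solely as influenza. Such a case would then be dropped, while the same presentation with a negative test keeps its bronchitis or pneumonia code and stays as a control. Other virus-specific codes, such as B97.x, are also driven by test results and would remain.

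**Conclusion.** The point stands in a limited form. As printed, the entry rule lets a positive influenza result create eligibility for admissions that would be ineligible if negative. That departs from what a test-negative design needs, and the protocol itself fixes it by giving the code list without an exception for influenza.

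The consequence is a possible bias in test-negative VE of unknown direction and amount. It requires both a non-zero share of influenza-code-only cases and a difference in their vaccination odds that survives adjustment. For a true VE of 40% and adult coverage of 45.7%, a 5-10% share with k from 0.5 to 2 moves VE by at most 3.5 points up or 4.6 points down. At a 30% share the range widens to about 10 points up and 15 points down. Share and odds ratio are assumptions; the protocol gives neither.

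The cohort VE analysis has no test-negative controls, so this asymmetry does not arise there.

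**What to change.** In section 6.1, Objective 5, under the test-negative design, add text to this effect:

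> The number and proportion of cases that qualify only on an influenza code (J09-J11 or the ICD-9 equivalents) will be reported. Two sensitivity analyses will apply one entry rule to cases and controls alike: (a) requiring a listed Appendix D code other than an influenza code; (b) as (a), but also admitting tested inpatients on the Appendix D sign and symptom codes, whatever the test result.

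Leave the primary entry rule and the cohort outcome definition unchanged.

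The cost is a short addition and a few extra runs on diagnosis codes that section 5.6 already has extracted. Analysis (a) is less precise and may drop respiratory cases coded solely as influenza, which is why it should not replace the primary rule. Analysis (b) brings in a less specific group of admissions, so it should be stratified on, or adjusted for, whether another listed code is present. If the count of influenza-code-only cases is negligible, the matter is closed by reporting it.

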### 4.1 Primary Objectives

1. Assess the validity and biases associated with defining the source population based on care-seeking.
  - Compare characteristics of the different cohorts, as defined above, assessing differences in the demographics, the frequency of underlying high-risk conditions, and the frequency of respiratory hospitalizations during influenza season.
2. Assess internal and external validity of influenza vaccination data for current and prior seasons.
  - Internal validity:
    - Assess the accuracy of the derived vaccine status variable in relation to a manual review of records on a subset of the cohort.
    - Describe the contributions to the overall conclusion about vaccination status by various sources from which vaccination data were obtained.
    - Describe the consistency of vaccination data that are available by data source, including date of vaccination, vaccine type, vaccine route, vaccine

lot number, setting in which vaccine was administered, number of doses of vaccine (children <9 years).

- Describe completeness of vaccination data (e.g. date of vaccination, type of vaccine, lot number) by data source for the current season and prior seasons.

- External validity:

- Compare vaccine coverage and data completeness to values reported from other studies with active enrollment / prospective data collection.

3. Assess biases associated with clinical testing for influenza and other respiratory viruses and whether they differ in the inpatient versus outpatient setting:

- Assess the accuracy of the extracted test dates, types, and results in relation to a manual review of records on a subset of the cohort.
- Estimate proportion of cohort enrollees tested for influenza and other respiratory viruses during the influenza season.
- Describe types of influenza and other respiratory virus tests performed on cohort enrollees by pediatric and adult age groups and how test types vary by setting.
- Estimate the proportion of respiratory hospitalizations tested for influenza during the influenza season and factors associated with influenza testing in the inpatient setting including age, high-risk conditions, current season influenza vaccination status, ICU stay, timing of encounter within season, diagnoses codes.

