- Estimate the proportion of outpatient visits for acute respiratory illness (ARI) that were tested for influenza and factors associated with influenza testing in the outpatient setting including age, high-risk conditions, current season influenza

vaccination status, visit type, timing of encounter within influenza season, diagnoses codes.

4. Measure the incidence of health outcomes related to influenza by pediatric and adult age groups as outlined below. The incidence of these outcomes will be assessed by age groups, demographic characteristics, influenza type/subtype, and high-risk conditions:
  - Laboratory confirmed influenza-associated respiratory hospitalizations.
  - ICU admission among persons with laboratory-confirmed influenza-associated respiratory hospitalizations.
  - Invasive mechanical ventilation use among persons with laboratory-confirmed influenza-associated respiratory hospitalizations.
  - In-hospital death among persons with laboratory-confirmed influenza-associated respiratory hospitalizations.
  - Laboratory-confirmed influenza among persons with outpatient visits for acute respiratory illness.
  
5. Estimate the effectiveness of current season influenza vaccine in preventing the below outcomes by age groups, influenza type/subtype, and high-risk conditions:
  - Laboratory confirmed influenza-associated respiratory hospitalizations (all ages).
  - ICU admission among persons with laboratory-confirmed influenza associated respiratory hospitalizations (all ages).
  - Laboratory-confirmed influenza among persons with outpatient visits for acute respiratory illness (pediatrics; adults if outpatient influenza testing permits).

Appendix A presents the main outcomes, exposures, and modifiers of interest for the primary and secondary study objectives. Appendix B provides the data dictionary of analytic variables needed to meet these objectives.

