***Objective 3: Biases associated with clinical testing***

- Describe the frequency of clinical testing for influenza and other respiratory viruses in the cohort during an influenza season by setting (inpatient vs. outpatient), age group, high-risk status, influenza vaccination, prior healthcare utilization, and timing of encounter within the season.
- Describe the diagnoses associated with visits where clinical testing for influenza and/or other viruses was performed.

- Among hospitalizations with respiratory illness during the influenza season, describe the frequency and types of clinical testing used.
  - Characteristics and predictors of receipt of diagnostic test for influenza will be assessed using bivariate tests of association and/or multivariate regression with receipt of test as outcome of interest and patient and clinical characteristics (including age, vaccination status, high-risk conditions, timing of the clinical encounter within the season, prior healthcare utilization, diagnoses, etc.)
- Among outpatient visits for ARI during the influenza season, we will describe the frequency and types of clinical testing used.
  - Characteristics and predictors of receipt of diagnostic test for influenza will be assessed using bivariate tests of association and/or multivariate regression with receipt of test as outcome of interest and patient and clinical characteristics (including age, vaccination status, high-risk conditions, timing of the clinical encounter within the season, prior healthcare utilization, diagnoses, etc.)

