| Encounter for screening for other viral diseases   | Z11.5 *                 |
| Encounter for screening for other viral diseases   | Z11.59 *                |
| Encounter for screening for other infectious and parasitic diseases                      | Z11.8 *                 |

|  |           |
|--|-----------|
| Encounter for screening for infectious and parasitic diseases, unspecified   | Z11.9 *   |
| Contact with and (suspected) exposure to other viral communicable diseases   | Z20.82 *  |
| Contact with and (suspected) exposure to other viral communicable diseases   | Z20.828 * |
| Contact with and (suspected) exposure to other communicable diseases   | Z20.89 *  |
| Contact with and (suspected) exposure to unspecified communicable disease  | Z20.9 *   |
| Mucocutaneous lymph node syndrome [Kawasaki]   | M30.3 *   |
| Encounters occurring in the outpatient clinic, telehealth, emergency department, or urgent care should additionally capture encounters with these codes           |           |
| Hemorrhage from respiratory passages, cough, abnormalities of breathing, pain in throat and chest, other symptoms/signs involving the circulatory and respiratory system | R04-R09 * |
| Fever  | R50 *     |
| Headache   | R51 *     |
| Malaise and fatigue  | R53 *     |
| Shock, unspecified   | R57.9 *   |
| Symptoms and signs specifically associated with systemic inflammation and infection  | R65 *     |
| Chills without fever   | R68.83 *  |

[figure not shown]
\*For the complete list these of codes, please refer to the data dictionary referenced in Appendix B.

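### Objective 3 compares influenza testing between settings on unlike denominators: sign and symptom codes can qualify an outpatient visit but not a hospitalization, so part of any difference may come from the definitions

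*Protocol*

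**What the plan says.** Section 4.1 sets Objective 3 as a comparison of settings: "Assess biases associated with clinical testing for influenza and other respiratory viruses and whether they differ in the inpatient versus outpatient setting". Two of its measures use encounters as the base:

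- Inpatient: "Estimate the proportion of respiratory hospitalizations tested for influenza during the influenza season".
- Outpatient: "Estimate the proportion of outpatient visits for acute respiratory illness (ARI) that were tested for influenza".

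Both measures also ask which factors are associated with being tested. Section 5.5 defines the two encounter types by the Appendix D codes. Section 6.1, Objective 3, describes testing in each setting and plans predictor analyses (bivariate tests, regression or both) separately for each, with diagnoses among the candidate predictors.

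The code lists are in Appendix D, under Respiratory Outpatient Visits and Hospitalizations. Codes count in any position. On the inpatient side, "For hospitalizations, only discharge codes should be considered". On the outpatient side, "Encounters occurring in the outpatient clinic, emergency department, urgent care, or via telehealth should additionally include encounters with codes related to signs/symptoms". The table repeats the rule above its last block, saying that non-inpatient encounters "should additionally capture encounters with these codes". That block covers respiratory and circulatory symptoms including cough (R04-R09), fever (R50), headache (R51), malaise and fatigue (R53), unspecified shock (R57.9), systemic inflammation signs (R65) and chills without fever (R68.83).

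**The concern.** The outpatient code set is the inpatient set plus seven sign and symptom rows. A clinic visit coded only for headache or fatigue enters the outpatient denominator. An admission whose discharge codes are only those does not enter the inpatient one. The two proportions tested therefore describe differently selected encounters.

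This bears on the question that the objective poses, "whether they differ in the inpatient versus outpatient setting". A reader who sets the two proportions, or the two sets of predictors, side by side cannot tell how much of a difference reflects testing practice and how much reflects which encounters were admitted to each denominator. The predictor models carry the same problem. If symptom-only coding varies with age or high-risk status, an apparent predictor of testing may partly describe who receives symptom codes. Section 6.1 plans no analysis on a shared code set and does not warn that the two proportions are not directly comparable.

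**Working it through.** The protocol states no testing proportion, power or sample size on this point, so there is no figure to reproduce. The check compares the code sets and then works through the arithmetic of a mixed denominator.

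**Step 1. Code sets (from Appendix D).** Inpatient: the common list, discharge codes, any position. Outpatient: the common list plus R04-R09, R50, R51, R53, R57.9, R65 and R68.83, any position. Outpatient visits thus fall into two groups: those with at least one common-list code, and those that qualify on a sign or symptom row alone. The second group has no inpatient counterpart.

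**Step 2. Formula.** Let s be the symptom-only share of outpatient visits, pc the proportion tested among common-list visits, and ps the proportion tested among symptom-only visits.

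- Outpatient proportion tested = (1 − s) × pc + s × ps.
- Shift relative to the common-list proportion = s × (ps − pc).

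With p_in for the inpatient proportion, the observed difference splits as p_in − [(1 − s) × pc + s × ps] = (p_in − pc) + s × (pc − ps). The first term compares the settings on the same rows. The second comes from the added rows.

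**Step 3. Inputs.** The protocol gives none of s, pc or ps. Assumed ranges: s of 10%, 30% and 50%; pc of 20% and 40%; ps/pc of 0.25, 0.5, 1.0 and 1.5.

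**Step 4. Shift in the outpatient proportion tested, in percentage points.**

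| pc | s | ps/pc 0.25 | 0.5 | 1.0 | 1.5 |
|---|---|---|---|---|---|
| 20% | 10% | −1.5 | −1.0 | 0 | +1.0 |
| 20% | 30% | −4.5 | −3.0 | 0 | +3.0 |
| 20% | 50% | −7.5 | −5.0 | 0 | +5.0 |
| 40% | 10% | −3.0 | −2.0 | 0 | +2.0 |
| 40% | 30% | −9.0 | −6.0 | 0 | +6.0 |
| 40% | 50% | −15.0 | −10.0 | 0 | +10.0 |

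Worked line: pc 40%, s 30%, ps/pc 0.5 gives 0.7 × 0.40 + 0.3 × 0.20 = 0.34, so 34% in place of 40%. With ps/pc 1.5 the same s gives 0.7 × 0.40 + 0.3 × 0.60 = 0.46.

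**Step 5. Predictors.** The same identity applies within each level of a characteristic. Take two age groups, both with pc 20% and ps 5%, so that testing does not depend on age within either type of visit. If s is 10% in one group and 30% in the other, the proportions tested are 0.9 × 0.20 + 0.1 × 0.05 = 18.5% and 0.7 × 0.20 + 0.3 × 0.05 = 15.5%. A 3-point age difference appears from coding alone.

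**Step 6. What is untouched.** Section 4.1 also asks for the proportion of cohort enrollees tested, and the first bullet of Section 6.1, Objective 3, describes testing in the cohort by setting. Both have the cohort as base and do not use these code lists.

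**The case against.** The strongest reply is that the difference is deliberate and openly stated. The wider outpatient list serves case finding, Objective 3 names two different encounter types, and Section 6.1 analyses them separately without a formal test of one proportion against the other. Appendix D calls its codes examples that may be modified and points to a data dictionary for the complete list, and a restricted-code table could sit in an analysis plan that is not shown. Diagnoses are already a candidate predictor, and encounter diagnosis codes are collected (Section 5.6), so the planned work could show whether symptom-coded visits are tested differently.

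Much of this stands: the list is a choice, not a contradiction, and should be kept. It does not settle the matter, because comparing settings is the stated question of the objective. Diagnosis as a predictor within each setting does not align the settings either: no hospitalization can enter on a symptom code alone, so they do not overlap in that group.

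A reader might infer three stronger things, which the protocol does not support:

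- **That the outpatient proportion will look too low.** This needs symptom-only visits to be tested less often. The added rows include cough and fever, which are plausible reasons to test, and the protocol has no data either way.
- **That all of Objective 3 is affected.** The cohort-based measures are not.
- **That the decision on adult outpatient VE is compromised.** Sections 4.1 and 6.1 make it depend on whether testing allows, but state no threshold and no link to the contrast between settings. The outpatient VE outcome in Section 5.5 uses the full outpatient list, so testing in those same visits is the relevant base for that judgement.

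**Conclusion.** The point holds in limited form. Objective 3's encounter-based proportions tested, and the predictor models built on the same encounters, are not like for like across settings, and part of any inpatient-outpatient difference may come from the code lists. The shift is s × (ps − pc). Its size and direction cannot be derived from the protocol. Under the assumed ranges it lies between −15 and +10 percentage points, and it vanishes if symptom-only visits are tested as often as the others. The asymmetry of the lists is certain from Appendix D; the magnitude rests wholly on assumed inputs. Because the comparison is a primary question and the remedy is nearly free, the change should be made.

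**What to change.** Add to Section 6.1, Objective 3, text to this effect: *When settings are compared, outpatient testing (proportion tested and its predictors) is also reported on the Appendix D rows common to both settings. Outpatient visits that qualify solely on sign or symptom rows are shown on a separate line.*

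Keep the full Appendix D outpatient list for case finding, for the main outpatient description, and for judging whether outpatient testing permits adult VE.

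The cost is one flag, derived from diagnosis codes already collected for outpatient respiratory encounters (Section 5.6), and one extra table line, plus a repeat of the outpatient predictor analysis on the shared rows. Appendix E has sites derive data elements before transfer, so the flag is best specified before extraction. There is a statistical price too: the shared-row line leaves out some genuine acute respiratory visits coded only as cough or fever. It therefore supplements the full-list result and does not replace it.
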